## Protocol Synopsis

**Protocol  
Number:**

2017-0196

**Title:** Effect of Wearable Health Technology on Patients Treated for Chronic Pain at Geisinger Health System

**Sponsor:** Purdue Pharma L.P.  
[name]  
[name]  
[name]

**Study Phase:** Phase 4

**Study Sites:** The study will be conducted in the United States at 1 site, the Multidisciplinary Pain Program at Geisinger Health System

**Indication:** Chronic Pain

**Background:** Care for the chronic pain patients can be challenging. Providers are dependent on patients' recall of their symptoms between visits to gauge disease severity and treatment progress. Providers often lack timely access to patients' data on symptom severity, thereby limiting the providers' ability to effectively manage and optimize long-term treatment regimens for their patients.

Recent use of wearable health technology (WHT) has been effective in improving patient outcomes. Many wearable biosensors and their applications have been introduced in different stand-alone or interactive formats. WHT apps may have interactive capabilities involving active health or behavior change information that collects data from the user. WHT can detect abnormal and unforeseen situations and monitor physiological parameters and symptoms through these trackers. This technology has transformed healthcare by allowing continuous monitoring of patients without hospitalization. Medical monitoring of patients' body temperature, heart rate, brain activity, muscle motion and other critical data can be delivered through these trackers. When integrated with an expert-directed chronic pain intervention program like Geisinger's Multidisciplinary Pain Program (MPP), WHT (eg iPhone, Apple Watch) may improve comprehensive patient management and outcomes for patients living with chronic disease. WHT can also provide real-time data, allowing a healthcare provider to engage in more proactive patient care.

**Objectives** To assess whether the addition of WHT to the Geisinger MPP leads to improvements in clinically meaningful patient outcomes, reductions in healthcare utilization and costs.

**Patient Population:** The study population will be adult ( $\geq 18$  to  $< 76$  years) chronic pain patients being treated at pain clinics in the Geisinger healthcare system.

There will be 3 study groups, a WHT treatment group, a concurrent Medical Pain Management (MPM) control, and an historic MPP control:

1. WHT treatment group: patients admitted to the MPP during a predefined 12-month period who consented to participate in the study.
2. MPM control group: patients from MPM clinics within Geisinger during the same 12-month period.
3. Historic MPP control group: patients who completed the MPP 12 months before the start of this study (ie, before WHT was introduced to the MPP in August 2017).

**Study Design:** This is a prospective, non-randomized, non-blinded trial with historic and concurrent controls to assess the effect of the addition of WHT (Apple Watch, iPhone, Pain App, and physician and patient dashboards) on patient and health system outcomes. The WHT intervention group will include patients enrolled in the Geisinger's MPP Program over 1 year, with 1 year of follow up. Patients in the WHT group will be compared to patients in 2 control groups: patients enrolled in the MPP in the preceding year (historic control group), and patients enrolled on the MPM over the same period (concurrent control group).

The WHT intervention will consist of the following:

- Patient and HCP tracking of patient-reported pain, pain management, disability, depression and medication usage over time
- Patient and HCP tracking of quality of sleep and activity over time
- Prompts to patients to engage in self-care, including non-pharmaceutical pain management therapies consistent with their MPP training
- HCP alerts if patients exceed pre-specified thresholds in pain or functioning

Patients will use the WHT 20 hours per day, every day for a period of 12 months.

Patients will attend study visits at baseline and months 2, 4, 6, 8, 10 and 12. Patients consented into the WHT group will participate in the study for 12 months from the day of enrollment.

Outcome data for control patients will be collected retrospectively from the electronic health record (EHR). Assessments will have occurred as part of their standard of care.

Twelve months of enrollment, with 12 months of follow-up, for a total of 24 months.

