Statistical Methods:	
For clinical outcomes (primary, secondary, and exploratory), the effects of WHT will be quantified by calculating the change from baseline in clinical outcome variables in the WHT group over 12 months. For primary and secondary outcomes that are measured in the WHT group plus at least 1 control group, generalized linear modeling or nonparametric methods (depending on the score distributions) will be used to compare outcomes across the cohorts. Patient demographic and clinical characteristics that differ between groups at baseline will be included in multivariate adjusted models.
 
Repeated measures models will be used to generate point estimates and 95% confidence intervals (CIs) for least square mean (LSM) differences, odds ratios (ORs), or risk ratios (RRs). Where appropriate an overall F statistic will be generated to compare the change in groups across the study period (interaction of group*time).
 
For the analysis of healthcare utilization, a log-link function with a Poisson or negative binomial distribution will be used. For cost outcomes, a log-link function with a gamma distribution will be used. Otherwise, the same techniques described above (eg, GLM methods to account for matched groups, estimates, and CIs) will be used.
 
For analysis related to clinical outcomes collected only in the WHT group, the effects of WHT will be quantified by calculating the change from baseline over 12 months and using repeated measures ANCOVA models to compare to the null hypothesis (0 change).

-----------------------------	---

**Date of Protocol:** 12 September 2017

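### Consent filters the WHT group only and completion may filter the historic MPP group, so selection stays confounded with the WHT effect, in an unknown direction against historic MPP

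*Combined protocol and SAP*

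**What the plan says.** All references are to the Protocol Synopsis.

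- **WHT group (Patient Population, item 1):** "patients admitted to the MPP during a predefined 12-month period who consented to participate in the study".
- **MPM control (item 2):** "patients from MPM clinics within Geisinger during the same 12-month period". No consent condition is stated.
- **Historic MPP control (item 3):** "patients who completed the MPP 12 months before the start of this study". Study Design describes the same group differently, as "patients enrolled in the MPP in the preceding year (historic control group").
- **What consent entails (Study Design):** "Patients will use the WHT 20 hours per day, every day for a period of 12 months", with study visits at baseline and at months 2, 4, 6, 8, 10 and 12.
- **Control data (Study Design):** "Outcome data for control patients will be collected retrospectively from the electronic health record (EHR").
- **Allocation (Study Design):** "prospective, non-randomized, non-blinded trial with historic and concurrent controls".
- **Confounding control (Statistical Methods):** "Patient demographic and clinical characteristics that differ between groups at baseline will be included in multivariate adjusted models". The same section refers once to matched groups and names no matching variables or method.

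The synopsis does not say how MPP patients who decline consent are to be counted, described or followed.

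**The concern.** The objective is the effect of adding WHT to the MPP. Of the two planned contrasts, only WHT versus historic MPP holds the program constant, and its two arms are formed by different rules. Entry to the WHT group needs admission plus agreement to a year of near-continuous device wear and six post-baseline visits. Entry to the historic group needs completion of the program, or only enrolment, depending on which paragraph is followed.

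Patients who accept that burden may differ from those who refuse in motivation, self-management or ease with technology. Such traits could plausibly affect the change in pain, depression score and opioid use, which are the primary endpoints. If so, part of any difference between arms reflects who was counted. Because nobody is assigned to record outcomes for decliners, the plan as written can neither detect nor bound that part.

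**Working it through.** **1. The plan's own figure.** The point rests on the group definitions, not on a stated number. The only relevant figure is the detectable NPS effect under Sample Size: 0.42 versus historic MPP and 0.35 versus MPM. Neither can be reproduced, because alpha, SD, within-patient correlation and the number of time points in the omnibus F test are not given. A rough back-calculation assumes two-sided alpha 0.05, 80% power, a simple two-group comparison and 10% drop-out (216 WHT, 900 MPM, 135 historic):

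- Historic MPP: SD = 0.42 / [(1.960 + 0.842) x sqrt(1/216 + 1/135)] = 1.37
- MPM: SD = 0.35 / [(1.960 + 0.842) x sqrt(1/216 + 1/900)] = 1.65

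These are plausibility values only.

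**2. The filters side by side.**

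| Group | Defining event | Consent | Source of outcomes |
|---|---|---|---|
| WHT | MPP admission | Required | Study visits and devices |
| Historic MPP | Completion (item 3) or enrolment (Study Design) | None stated | EHR, retrospective |
| MPM | MPM clinic patient | None stated | EHR, retrospective |
| Decliners in the WHT year | MPP admission | Refused | In no group |

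**3. Bias against an all-comer control.** Let c be the consent rate and d the consenter-minus-decliner difference in expected improvement without WHT. If consenters improve by m, decliners improve by m - d, and all-comers by c x m + (1 - c)(m - d) = m - (1 - c)d. With no WHT effect, consenters minus all-comers is therefore

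bias = (1 - c) x d.

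Both inputs are assumptions:

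| c | d (NPS points) | Bias |
|---|---|---|
| 0.80 | 0.4 | 0.20 x 0.4 = 0.08 |
| 0.60 | 0.6 | 0.40 x 0.6 = 0.24 |
| 0.50 | 0.8 | 0.50 x 0.8 = 0.40 |

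If d is zero the bias is zero; if d is negative it runs against WHT.

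**4. Bias against completers.** If the historic group is completers, and they improve by s more than all admissions, then

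net bias = (1 - c) x d - s.

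In the middle row, s = 0.24 cancels the bias and a larger s reverses it. The documents give no value for c, d or s, so the sign is not determined.

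**5. MPM control.** The contrast is the WHT effect, plus the difference between MPP and MPM care and patients, plus consent selection. Consent selection is an extra term there.

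**6. What a residual bias would do.** Under the step 1 assumptions and no true WHT effect, a bias equal to a fraction f of the detectable effect shifts the test statistic by f x 2.80. Rejection probabilities, against a nominal 0.05, are:

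| f | NPS points vs historic MPP | Probability of a significant result |
|---|---|---|
| 0.25 | 0.11 | 0.11 |
| 0.50 | 0.21 | 0.29 |
| 0.75 | 0.32 | 0.56 |
| 1.00 | 0.42 | 0.80 |

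**The case against.** Several counter-arguments are fair.

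- **The historic group is itself selected.** Under item 3 an MPP patient who dropped out of the program is not counted, and completion may select for the same traits as consent. A reader might infer that both controls are unselected and that volunteer selection must therefore flatter WHT. The documents do not support that reading for historic MPP. This objection stands and removes any claim about direction. It does not remove the problem, since two different unmeasured filters cannot be assumed to cancel.
- **Adjustment and matching are planned.** It would be too strong to say that all volunteer selection is counted as a WHT effect, because measured baseline differences enter the models. What remains is the unmeasured part. The synopsis does not list EHR fields, so one cannot say that motivation is unrecorded; but the plan names no such variable, and its matching is undefined.
- **Endpoints are changes from baseline.** Stable differences in level therefore do not bias them by themselves. That is correct, but differences in the rate of change still do.
- **The sizes are assumed.** The chosen values of d exclude small, zero and negative differences. A reader might divide 0.08-0.40 by 0.42 and conclude that 19% to 95% of the detectable effect could be bias. The division is correct, but the inputs are assumed, the formula needs an all-comer control, and 0.42 belongs to an omnibus test of differences at any time. It should not be quoted as an estimate.
- **The text is a synopsis.** Its silence on decliners is weak evidence about any fuller document. If a provision exists elsewhere, citing it would settle that part.

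**Conclusion.** The point holds as a design weakness that should be corrected. Consent is a condition for WHT only, the defining event of the historic group is stated in two incompatible ways, decliners are in no group, and no planned step addresses willingness to take part. In a non-randomized comparison, residual selection is then inseparable from the WHT effect.

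The documents support neither a direction nor a size against historic MPP. Against MPM, consent selection comes on top of a difference in care that is already confounded with WHT. The range of 0.08-0.40 NPS points is an illustration that depends on 50-80% consent, a 0.4-0.8 point difference and an all-comer control. It shows only that a modest difference between consenters and decliners could matter beside detectable effects of 0.35 and 0.42.

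**What to change.** 1. **Reconcile the historic definition.** Resolve *completed* versus *enrolled*, and define both MPP groups by the same event, admission to the program.
2. **Account for decliners.** Identify all eligible MPP admissions in the WHT window and report the consent rate. Extract decliners' EHR outcomes under the approvals used for the control extract, where these permit it for people who refused.
3. **Describe the selection.** Tabulate baseline and 12-month EHR outcomes for consenters and decliners.
4. **Add a supporting analysis.** Compare all MPP admissions in the WHT window with all MPP admissions in the historic window, using EHR outcomes in both. Report it with confidence intervals beside the consenters-only result.
5. **State the interpretation in advance.** If the all-admissions analysis does not support the consenters-only result, describe the latter as possibly affected by volunteer selection. A rule requiring only agreement in direction would be too weak: with no effect and no calendar trend, the all-admissions estimate favours WHT about half the time, and more often when the consenter result does, because the patients overlap.

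**Cost:** one further retrospective extract of the kind already planned for controls, a check that approvals cover decliners, one table and one model. Enrolment and the intervention are unchanged. The all-admissions estimate is diluted by non-users and does not remove calendar-time differences, so it supports the consenter analysis and does not replace it.

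### The Protocol Synopsis selects the historic MPP control by completion in one place and by enrollment in another, which leaves the historic baseline date open

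*Combined protocol and SAP*

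**What the plan says.** All the relevant text is in the Protocol Synopsis of the combined protocol and SAP.

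- **Historic control, Patient Population item 3:** "patients who completed the MPP 12 months before the start of this study", with the gloss that this means "before WHT was introduced to the MPP in August 2017".
- **Historic control, Study Design:** "patients enrolled in the MPP in the preceding year (historic control group").
- **WHT group, Patient Population item 1:** "patients admitted to the MPP during a predefined 12-month period who consented to participate in the study". Study Design also defines this group by enrollment in the "MPP Program over 1 year, with 1 year of follow up".
- **WHT clock, Study Design:** "Patients consented into the WHT group will participate in the study for 12 months from the day of enrollment", with a baseline visit.
- **MPM control:** item 2 takes "patients from MPM clinics within Geisinger during the same 12-month period". Study Design describes the same group as enrolled over that period.
- **Control data, Study Design:** "Outcome data for control patients will be collected retrospectively from the electronic health record (EHR").

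Outcome Measures defines all the Aim 1 comparisons, including the three primary endpoints, as differences in change between baseline and month 12. Statistical Methods adjusts for characteristics found to differ between groups at baseline.

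**The concern.** The objective is the effect of adding WHT to the MPP. WHT versus historic MPP is the only contrast in which both groups are in that programme, so the definition of its control matters most.

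Completion happens after entry. Under item 3, patients who entered the MPP and did not finish are left out of the control, while no rule leaves their counterparts out of the WHT group. If completers and non-completers differ in how pain, depression or medication use changes, part of the between-group difference would reflect that selection.

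The baseline is a second problem. If the historic baseline is taken at completion, the control's change score omits whatever change took place during the programme. The WHT change score may include it, depending on when in the MPP a patient is enrolled in the study.

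Covariate adjustment does not settle either problem. It needs the baseline date that is in dispute, and it cannot be relied on to remove selection on a later event. Because control data are extracted retrospectively, two analysts following the synopsis could draw different control groups with different baselines.

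**Working it through.** No stated figure in the plan depends on this point, so there is none to reproduce. The check compares the two rules on a calendar.

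**Inputs.** From the synopsis: selection by completion (item 3) or enrollment (Study Design); a 12-month span; WHT introduced in August 2017; 12 months from baseline for every Aim 1 comparison. Assumed: study start is month 0 and falls in August 2017; patients enter uniformly over time; every patient completes after the same programme length L, in months. The documents do not give L, so a range is shown.

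**Enrollment rule.** Enrollment falls in months −12 to 0.

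**Item 3, literal reading** (completed at least 12 months before start). Completion is at or before month −12, so enrollment was earlier still. No patient meets both rules.

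**Item 3, window reading** (completed during the 12 months before start). Completion in months −12 to 0 means enrollment in months −12−L to −L. The part of the enrollment window in common is (12 − L)/12 for L up to 12.

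| Assumed L | Enrollment months under item 3 | Months in common | Share |
|---|---|---|---|
| 0 | −12 to 0 | 12 | 100% |
| 1 | −13 to −1 | 11 | 92% |
| 2 | −14 to −2 | 10 | 83% |
| 3 | −15 to −3 | 9 | 75% |
| 6 | −18 to −6 | 6 | 50% |
| 12 | −24 to −12 | 0 | 0% |

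The rules coincide only at L = 0. This is with everyone completing; non-completers would be a further difference, since only the enrollment rule admits them.

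**Calendar position of follow-up.** A patient enrolled at month e, between −12 and 0, is followed to month e + 12, so e + 12 months fall after study start. With uniform entry the mean of e is −6, giving −6 + 12 = 6 of 12 months. The window reading of item 3 with the clock started at completion gives the same 6 months. The literal reading with the clock at completion gives 0.

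**Baseline date.** The WHT start is stated. For the historic group, Study Design points to enrollment and item 3 to completion; no sentence chooses between them.

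**The case against.** The strongest reply is that the two sentences are loose descriptions of one cohort. On the window reading, a patient who enrolled and completed in the preceding year meets both rules, and for a programme of 1 to 2 months the windows share 92% to 83%. This stands in part: a reader might infer that the definitions are mutually exclusive, but that holds only on the literal reading. They are still different rules, and neither the reading nor the programme length is stated.

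A reader might also infer that the controls have no patient-level clock at all. The documents do not support that. Study Design names enrollment for all three groups, including the MPM control, and Outcome Measures implies a 12-month horizon for all. For the MPM group, what is missing is mainly an explicit index date and baseline window, which a synopsis may leave out. For the historic group the difficulty is a conflict, not only an omission.

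Headcounts can make the problem look larger than shown. The historic group is 150 of 240 + 150 = 390 patients in its contrast (38.5%), and the two control groups are 1,150 of 1,390 planned patients (82.7%). These are group sizes. They do not count misclassified patients or measure bias, and many historic patients may satisfy both rules.

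It is also fair to say that MPP entry cannot simply be prescribed as the historic index date. Nothing shows that WHT study enrollment coincides with MPP admission, and the WHT prompts are described as consistent with MPP training, so enrollment could follow some of it. The fix below is conditional for that reason.

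Finally, item 3's gloss signals a wish for a control untouched by WHT. That aim is reasonable, but restricting the control to completers is not needed to meet it.

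**Conclusion.** Wrong as written, and it should be fixed. The synopsis holds two different selection rules for the historic MPP control and does not say which applies. If item 3 is followed, the control is selected on a post-entry event and the WHT group is not. If Study Design is followed, that selection does not arise. The historic baseline date is left between enrollment and completion.

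The size and direction of any bias cannot be determined: the documents give no programme length, completion rate or difference between completers and non-completers. The plan's detectable NPS difference for this contrast is 0.42, and nothing in the documents shows whether a bias would be larger or smaller than that. The overlap shares rest on the assumed programme lengths, full completion and uniform entry. The figure of about 6 of 12 follow-up months after the introduction of WHT rests on uniform entry and an August 2017 start. It describes calendar overlap, not demonstrated WHT use by historic patients.

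The conclusion is limited to the synopsis supplied.

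**What to change.** 1. **Reconcile the definitions.** Reword item 3 to select on MPP enrollment, as Study Design does and as the WHT group is selected. For example: *patients enrolled in the MPP from [date] to [date], all before WHT was introduced, whether or not they completed the programme.* Give exact calendar dates.
2. **State the index date.** Set it for historic patients at the same point in the MPP pathway as WHT enrollment: MPP entry if WHT enrollment takes place at admission, otherwise the matching later point, with the same eligibility applied to both groups. State enrollment as the MPM index date for consistency.
3. **Report MPP completion in both MPP groups**, with a completers-only sensitivity analysis applied to both.
4. **Address follow-up past August 2017.** Report any WHT use by historic patients, and add a sensitivity analysis with an earlier historic window.

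The cost is protocol wording and a changed record query. No prospective patients are added, and the WHT clock and visit schedule stay as they are. The number of historic patients returned may change and must be rechecked against the planned 150. Month-12 values may be missing more often among non-completers. Differences between the groups in consent, calendar period and data capture remain and should be stated as limitations.

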**Estimated Study Duration:**

Outcome Measures:	Study Aim 1 (Between- Group Differences)
	
 
• Primary Clinical Endpoints 
 
○ A difference in the change in pain scores over time from baseline to month 12 (M12) as measured by the Numerical Pain Score (NPS)
 
○ A difference in the change in depression scores over time from baseline to M12 as measured by the Patient Health Questionnaire (PHQ-9)
 
○ A difference in the change in pain medication use over time from baseline to M12, calculated as mean daily morphine equivalents (MEQs)
 
 
 
• Secondary Clinical Endpoints 
 
○ A difference in the change in physical function/disability over time from baseline to M12 as measured by the Oswestry Disability Index (ODI)
 
 
 
• Endpoints Related to Resource Utilization 
 
○ A difference in the change in healthcare resource utilization over time (quarterly) from baseline to M12: number of hospitalizations, emergency department (ED) visits, inpatient, outpatient visits, rehabilitation visits, and pharmacy/medication orders
 
○ A difference in the change in healthcare costs over time (quarterly) from baseline to M12: total, inpatient, outpatient, rehabilitation, and pharmacy
 
 
 

	Study Aim 2 Comparisons within WHT Group

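### Scheduled study visits exist only in the WHT group, and the plan has no rule to separate them from routine care in the outpatient-visit and cost endpoints

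*Combined protocol and SAP*

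**What the plan says.** All references are to the Protocol Synopsis.

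- **Objectives.** Besides better patient outcomes, the trial looks for "reductions in healthcare utilization and costs".
- **Study Design, visits.** "Patients will attend study visits at baseline and months 2, 4, 6, 8, 10 and 12". The next sentence is "Patients consented into the WHT group will participate in the study for 12 months from the day of enrollment".
- **Study Design, controls.** Outcome data for both control groups are taken retrospectively from the electronic health record. Of the control assessments it says "Assessments will have occurred as part of their standard of care". Their number and timing are not given.
- **Outcome Measures, Endpoints Related to Resource Utilization.** The between-group comparison of quarterly change covers "number of hospitalizations, emergency department (ED) visits, inpatient, outpatient visits, rehabilitation visits, and pharmacy/medication orders". The cost endpoint is "A difference in the change in healthcare costs over time (quarterly) from baseline to M12: total, inpatient, outpatient, rehabilitation, and pharmacy".
- **Statistical Methods.** "For the analysis of healthcare utilization, a log-link function with a Poisson or negative binomial distribution will be used". Costs use a log link with a gamma distribution. Baseline characteristics that differ between groups enter the adjusted models. Nothing is said about encounters that arise from the study itself.

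**The concern.** The visit sentence says only that patients attend. Read with the sentences on WHT consent and retrospective control data, it can describe only the WHT group. The visit schedule is therefore completely tied to group, and an outpatient visit is itself an outcome. Any study visit that is recorded as an encounter and would not otherwise have happened adds to the WHT count and, if charged, to outpatient and total cost.

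The planned analysis does not remove this. The six visits fall after baseline, so they enter the WHT group's change. No baseline covariate carries the visit schedule. A larger sample only makes a biased ratio look more precise.

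What is at stake is one of the trial's stated aims: a real fall in outpatient use or cost could be diluted, hidden or shown as a rise.

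**Working it through.** **The plan's own figure.** There is none to reproduce. The Sample Size section gives detectable effects for the primary clinical outcomes only, none for utilisation or cost.

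**Inputs from the document.** There are six post-baseline visits (months 2, 4, 6, 8, 10, 12) in the WHT group and none in the controls. Outcomes are quarterly.

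**Assumed inputs.** The routine outpatient rate *r* is not given; 6 to 36 visits a year are shown. The number *a* of the six visits that are both recorded and additional is not given either; 0 to 6 are shown. The other *s* = 6 − *a* are taken to replace routine visits one for one.

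**Step 1. Annual rate ratio, no true effect:** (*r* + *a*)/*r*.

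| Routine visits a year | *a* = 6 | *a* = 3 | *a* = 2 | *a* = 0 |
|---|---|---|---|---|
| 6 | 2.00 | 1.50 | 1.33 | 1.00 |
| 8 | 1.75 | 1.38 | 1.25 | 1.00 |
| 12 | 1.50 | 1.25 | 1.17 | 1.00 |
| 24 | 1.25 | 1.13 | 1.08 | 1.00 |
| 36 | 1.17 | 1.08 | 1.06 | 1.00 |

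If the visits are not recorded as encounters and replace nothing, the ratio is also 1.00.

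**Step 2. A true 20% reduction:** (0.8*r* + *a*)/*r*. With *a* = 6 it appears as 1.80, 1.30, 1.05 and 0.97 at *r* = 6, 12, 24 and 36. With *a* = 2 and *r* = 24 it is (19.2 + 2)/24 = 0.88, diluted but still a reduction.

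**Step 3. Change by quarter.** The endpoint is a change, and the utilisation baseline is not defined. If month 6 counts in the second quarter and month 12 in the fourth, the visits fall 1, 2, 1, 2. If the first quarter is the reference and all six are additional, the spurious ratio in quarters 2 and 4 is (*r*/4 + 2)/(*r*/4 + 1):

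- *r* = 6: 3.5/2.5 = 1.40
- *r* = 8: 4/3 = 1.33
- *r* = 12: 5/4 = 1.25
- *r* = 24: 8/7 = 1.14
- *r* = 36: 11/10 = 1.10

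In quarter 3 it is 1.00. The annual ratios in Step 1 apply on average only if baseline is a period before enrolment without study visits.

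**Step 4. Does dropping every study visit cure it?** With no true effect, dropping all six gives (*r* − *s*)/*r*. If half replace routine care (*s* = 3), this is 9/12 = 0.75 at 12 visits a year and 3/6 = 0.50 at 6: a false reduction in favour of WHT.

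**Step 5. Bounds.** For a true ratio θ, counting everything gives θ + *a*/*r* and dropping all study visits gives θ − *s*/*r*. The truth lies between the two, provided that visits replacing routine care are recorded. At *r* = 12, *s* = 3 and θ = 1, the bounds are 0.75 and 1.25.

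**Cost.** No cost ratio can be computed: the document gives no unit cost and does not say whether study visits are charged.

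**The case against.** The strongest reply is that the mechanism depends on two facts the synopsis does not state: that study visits are recorded as outpatient encounters, and that they add to routine care. WHT patients are in the pain programme anyway, and control patients also had routine assessment contacts, so study visits may largely coincide with ordinary follow-up. With full overlap the ratio is 1.00. This stands, and it is why the point is conditional and 1.00 belongs in the range.

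The routine rates are also assumed, and the endpoint is not limited to pain-clinic visits, so the true rate may be high and the distortion small. That stands too. A reader might infer from the 12-a-year row that a 20% reduction would be reported as a 30% increase. That is one scenario, with all six visits additional, and the document supports it no better than the scenarios where the reduction survives.

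Third, total cost also includes inpatient, rehabilitation and pharmacy components, and nothing shows that six visits would move it materially. That stands: the direction can be argued, but not the amount.

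Finally, the bias runs against WHT, so it cannot by itself create a false claim of benefit. This is correct for the count of all encounters. It fails for the obvious remedy of excluding every study visit, which can favour WHT (Step 4).

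None of this supplies a counting rule. Because overlap and recording are unsettled, outpatient results could not be interpreted without one.

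**Conclusion.** The concern holds as a gap in how encounters are counted, with a possible bias against WHT in outpatient visits, outpatient cost and total cost. Hospitalizations and emergency visits are not directly affected, nor are the primary clinical endpoints.

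The size cannot be derived from the document. At assumed routine rates of 6 to 36 a year, the annual null ratio runs from 1.00 to 2.00; with all six visits additional it is still 1.17 at 36 a year. On a change-from-first-quarter basis the distortion is smaller, at most 1.40 over the same rates, and alternates between quarters.

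A reader might infer that the trial will produce a spurious increase, or that every study visit counts as utilisation caused by WHT. The document does not support either: it is silent on recording and on overlap with routine follow-up. The supported conclusion is that the plan, followed as written, has no means of telling study-driven encounters from care, and that this should be settled before the utilisation and cost analyses are run.

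**What to change.** 1. Flag every scheduled study visit in the encounter and cost data.
2. By a rule fixed before analysis and applied without sight of outcomes, exclude from the main utilisation and cost analysis those encounters that were solely for study purposes. Keep those that also delivered routine care, and those triggered by WHT alerts, since alerts are part of the intervention.
3. Report two bounding analyses: one counting all encounters, one excluding all scheduled study visits. Claim an increase or reduction in outpatient visits, outpatient cost or total cost only if it holds in both.
4. Define the utilisation baseline as a period before enrolment that is free of study visits.

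The cost is some extra coding, including classification of each study visit, and a wider reported range for these endpoints. No additional patients or procedures are needed.
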